4.3.2.3.3 Unsolicited Non-serious Adverse Events From Day 0 to Day 30 After Vaccination

In addition to recording solicited reactions, subjects or parents / guardians will be instructed to record any other medical events that may occur during the 30-day period after vaccination. Space will be provided in the diary card for this purpose.

For each unsolicited non-serious AE, the following information is to be recorded:

- Start and stop dates^a
- Intensity of the event:
 - For measurable unsolicited non-serious AEs that are part of the list of solicited reactions, the size of the AE as well as the temperature for fever will be collected and analyzed based on the corresponding scale used for solicited reactions (see Table 4.1 and Table 4.2)
 - Other unsolicited non-serious AEs will be classified according to the following intensity scale:
 - Grade 1: No interference with activity
 - Grade 2: Some interference with activity
 - Grade 3: Significant; prevents daily activity
- Action taken for each AE, if any (e.g., medication)

The action taken by the subject or parent / guardian to treat any **unsolicited AEs** will be classified in the CRF using the following scale:

- 0: None
- 1: Medication (self-medication with an existing prescription or over-the-counter medication)
- 2: Health care provider contact (no new medication prescribed)
- 3: Health care provider contact and prescription of a new medication (health care provider instructed subject to take a new medication, either an over-the-counter medication or one requiring a written prescription)

^a The stop date of all related AEs will be actively solicited. For other events, the investigator will provide the stop date when it becomes available. AEs for which no stop date was obtained during the course of the trial will be considered as ongoing at the end of the trial.

- Whether the AE led to discontinuation
- Whether the AE was related to vaccination (for unsolicited systemic AEs)

4.3.2.3.4 Serious Adverse Events

Information on SAEs will be collected and assessed throughout the trial, from inclusion until 180 days (+14 days) after vaccination.

Any SAE occurring at any time during the trial will be reported by the Investigator through the electronic data capture (EDC) system and according to the completion guidelines provided by the Sponsor. All information concerning the SAE is to be reported, either as part of the initial reporting or during follow-up reporting if relevant information became available later (e.g., outcome, medical history, results of investigations, copy of hospitalization reports). The Investigator will assess the causal relationship between the SAE and the investigational product as either “Not related” or “Related”, as described in Section 4.3.2.3.7.

See protocol for further details on SAE reporting.

4.3.2.3.5 [REDACTED]

Not applicable.

4.3.2.3.6 Medically-Attended Adverse Events

MAAE information will be collected throughout the study. MAAEs that occur from Visit 1 (D0) to Visit 2 (D30[+14days]) will be recorded as unsolicited AEs on the diary card where the action taken category is 2 or 3 as part of all unsolicited AEs collected for this post-vaccination period. MAAEs that occur from Visit 2 (D30 [+14 days]) to D180 (+14 days) will be recorded as such in the MA. An MAAE that occurs within the study period but meets the definition of an SAE should be reported only on the SAE Reporting Form, but not on the MAAE page of the CRF. The Investigator will assess the causal relationship between the MAAE and the investigational or study product as either “Not related” or “Related”, as described in Section 4.3.2.3.7.

4.3.2.3.7 Assessment of Causality

The Investigator will assess the *causal relationship* between each unsolicited systemic AE and vaccination as either not related or related, based on the following definitions^a:

- 0: Not related – The AE is clearly / most probably caused by other etiologies such as subject’s underlying condition, therapeutic intervention, or concomitant therapy; or the delay between vaccination and the onset of the AE is incompatible with a causal relationship; or the AE started before the vaccination (screening phase, if applicable)

^a ICH Guidelines, Clinical Safety Data Management E2A

- 1: Related – There is a “reasonable possibility” that the AE was caused by the vaccination, meaning that there is evidence or arguments to suggest a causal relationship

Note: By convention, all injection site AEs (solicited and unsolicited) and all solicited systemic reactions are considered to be related to vaccination and referred to as reactions, and therefore do not require the Investigator’s opinion on relatedness.

AEs likely to be related to the product, whether serious or not, that persist at the end of the trial will be followed up by the Investigator until their complete disappearance or the stabilization of the subject’s condition. The Investigator will inform the Sponsor of the date of final disappearance of the event.

4.4 Derived Endpoints: Calculation Methods

4.4.1 Safety

4.4.1.1 Solicited Reactions

4.4.1.1.1 Daily Intensity

All daily records for solicited reactions will be derived into daily intensity according to the following classification: None, Grade 1, Grade 2, Grade 3, or Missing.

For the derivation of daily intensities the following sequential steps will be applied:

- 1) Solicited reactions (except Fever/Pyrexia) with an investigator presence recorded as “No” and with all daily records missing then all daily intensities will be derived as None.
- 2) For a temperature partially missing after decimal point, the data will be analyzed replacing “MD” (missing data) by zero. For example, a “39.MD” daily temperature will be considered as "39.0°C" at the time of analysis.
- 3) For non-measurable (NM) solicited reactions, daily intensities will correspond to daily records reported in the clinical database. For measurable solicited reactions the daily measurements reported in the clinical database will be converted based upon the intensity scales defined in the protocol; this assumes a reaction that is too large to measure (NM) is Grade 3. Note the intensity could be considered “None” (not a reaction) in the analysis despite being considered a reaction by the investigator (e.g., swelling measurement > 0 mm but < 25 mm in adults).

Note: The maximum intensity on the ongoing period is derived from the record of the maximum intensity/measurement after the end of the solicited period following the rule described above.

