4.4.1.1.2 Maximum Overall Intensity

Maximum overall intensity is derived from the daily intensities computed as described in Section 4.4.1.1.1 and is calculated as the maximum of the daily intensities over the period considered.

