4.4.1.1.3 Presence

Presence is derived from the maximum overall intensity on the period considered:

- None: No presence
- Grade 1, Grade 2, or Grade 3: Presence
- Missing: Missing presence

Subjects with at least one non-missing presence for a specific endpoint will be included in the analysis. Conversely, those without a non-missing presence will not be included in the analysis of the endpoint.

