5.3.1.4 Intensity

For solicited reactions, missing intensities will be handled as described in Section 4.4.1.1.1. For unsolicited non-serious AEs, missing intensities will remain missing and will not be imputed.

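### The SAP keeps an ungraded investigator 'No' as a non-reactor but has no rule for an ungraded 'Yes', so any such reactor drops out and lowers that solicited reaction rate

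*SAP*

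**What the plan says.** SAP 4.4.1.1.1 derives daily intensity in sequential steps. Step 1 covers every solicited reaction but fever, and only where the investigator's presence answer is 'No'. For a subject with that answer "and with all daily records missing then all daily intensities will be derived as None". Step 3 then takes intensity from the diary data alone: "For non-measurable (NM) solicited reactions, daily intensities will correspond to daily records reported in the clinical database", and measured reactions are converted from their daily measurements.

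Under 4.4.1.1.2 the overall intensity "is calculated as the maximum of the daily intensities over the period considered". Under 4.4.1.1.3, "Presence is derived from the maximum overall intensity on the period considered": None gives no presence, Grades 1 to 3 give presence, and Missing gives missing presence. The section ends: "Conversely, those without a non-missing presence will not be included in the analysis of the endpoint".

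The missing-data section adds nothing on this point. SAP 5.3.1.4 says "For solicited reactions, missing intensities will be handled as described in Section 4.4.1.1.1". No other section gives a rule for an investigator's 'Yes' that has no grade.

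**The concern.** Two subjects can have the same empty diary grid and each have a recorded answer. The one who answered 'No' is kept and the one who answered 'Yes' is lost, so whether a subject is analysed depends on the outcome.

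For pain, headache, malaise and myalgia, grade uncertainty does not justify this. Grade 1 in SAP Tables 4.1 and 4.2 covers a reaction that does not interfere with activity, so any genuine 'Yes' is at least Grade 1. Missing causality, by contrast, is resolved conservatively in SAP 5.3.1.2, where it counts as related.

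Describing the safety profile is a stated objective, and the percentages of subjects with each solicited reaction, with 95% CIs, are its main output. What is at stake is a possible understatement of those percentages.

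**Working it through.** The documents state no figure on this point, so there is none to reproduce.

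**1. Tracing the two cases through the SAP**

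| Section | 'No', no daily records | 'Yes', no daily records |
|---|---|---|
| 4.4.1.1.1 | None on every day (step 1) | No step uses 'Yes'; step 3 follows the empty records, so Missing |
| 4.4.1.1.2 | Maximum None | Maximum Missing |
| 4.4.1.1.3 | No presence, kept | Missing presence, left out of the endpoint |

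**2. Direction.** For one reaction, let N be the subjects with a presence answer or daily records, R those with a recorded Grade 1 or higher, and Y those marked 'Yes' with no daily records.

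- Rate under the SAP: R/(N−Y).
- Rate with 'Yes' counted as present: (R+Y)/N.
- Cross-multiplying, the first is smaller when Y(N−R−Y) > 0, that is, whenever Y > 0 and R+Y < N.

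The gap depends on Y, not on how many 'No' subjects have empty grids.

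**3. Illustration.** N = 3 × 900 = 2700 comes from the Protocol synopsis; R = 810 is assumed.

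| Y | R/(N−Y) | (R+Y)/N |
|---|---|---|
| 1 | 810/2699 = 30.01% | 811/2700 = 30.04% |
| 27 | 810/2673 = 30.3% | 837/2700 = 31.0% |
| 54 | 810/2646 = 30.6% | 864/2700 = 32.0% |

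**4. Size if loss is unrelated to reaction status.** Let r be the true rate and m the share of subjects with no daily records, both assumed. Then Y = mrN and R = (1−m)rN, so the SAP rate is (1−m)r/(1−mr). For r = 30% and m = 2%: 0.294/0.994 = 29.6%.

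| True rate | m = 1% | m = 2% | m = 5% |
|---|---|---|---|
| 5% | 4.95% | 4.90% | 4.76% |
| 30% | 29.8% | 29.6% | 28.9% |
| 45% | 44.8% | 44.5% | 43.7% |

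At 2% loss the shortfalls are 0.10, 0.42 and 0.50 points.

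**5. Extreme case.** If every subject with no daily records is a 'Yes', the SAP rate is (r−m)/(1−m). For r = 30% this gives 29.3%, 28.6% and 26.3% at m = 1%, 2% and 5%.

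**6. Precision for scale.** The Clopper-Pearson 95% CI is 28.3% to 31.8% for 810/2700 and 26.4% to 33.8% for 180/600, half-widths of about 1.7 and 3.7 points.

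**7. Erythema and swelling.** SAP 4.4.1.1.1 allows a reaction noted by the investigator to be analysed as None if it is below 25 mm. With q the probability that a 'Yes' reaches 25 mm, the comparator is (R+qY)/N, and the SAP rate is lower only when q > R/(N−Y). That holds if size is unrelated to diary loss. With 10% 'Yes', q = 0.5 and 2% loss (all assumed), the SAP rate is 4.91% against 5.00%.

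**8. Partly empty diaries.** SAP 4.4.1.1.2 does not say how Missing combines with None. If missing days are skipped, a 'Yes' whose reaction day is ungraded and whose other days are None becomes no presence. If a missing day makes the maximum Missing, the subject is left out. The text does not settle which applies.

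**The case against.** The strongest reply is that the SAP never says an ungraded 'Yes' is dropped, and that such cases should hardly exist. Protocol 13.2 has the coordinator obtain verbal clarification of missing or discrepant diary data. Protocol 9.3.2.3 has the investigator go through solicited reactions at Visit 2. Protocol 11.1 requires explanations for missing information, and 11.2 applies consistency checks. Step 1 may also only code a CRF whose daily grid is left blank once 'No' is entered. The CRF is not among the documents, so this cannot be checked. Finally, SAP 4.4.1.1.7 deliberately prefers the measurement to the investigator's ongoing flag.

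Much of this stands. The omission is inferred by chaining sections, the bias is zero if no such subject remains, and queries should keep the number low. But none of these safeguards gives a remaining 'Yes' a place in the analysis. If step 1 is only CRF coding, the gap is unchanged, because it depends on Y alone. Preferring a measurement to a flag is no reason where no measurement exists, and it has little bearing on pain, headache, malaise or myalgia.

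A reader might infer more than the documents support:

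- *That solicited rates are biased downward as a fact, by a point or more.* This needs ungraded 'Yes' cases in numbers that no section supports. Losses of 5% or 10% are assumptions.
- *That the MenACYW versus Menactra contrast is distorted.* The rule is the same in all groups, subjects and investigators are blinded, and safety is descriptive with no hypothesis tested. A shift needs such cases to differ by arm, and nothing indicates that they do.
- *That partly graded reactors are definitely reported as non-reactors.* This rests on one reading of an undefined maximum.
- *That every ungraded 'Yes' is a reaction.* For erythema and swelling it may be below 25 mm.

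**Conclusion.** The point holds in conditional form. Followed as written, the SAP uses the investigator's answer only when it is 'No'. Any subject with 'Yes' and no daily records is left out of that endpoint, which lowers the reported rate. The direction is certain for pain, headache, malaise and myalgia once one such subject exists and not everyone reacts. For erythema and swelling it also requires that size be unrelated to diary loss, or at least that q exceed the reported rate.

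The size cannot be computed from the documents. With 2% of subjects lacking daily records, unrelated to reaction status, it is about 0.5 point or less. If all of that 2% were reactors, a true 30% would be reported as 28.6%. The loss is per reaction, so a subject may still count in a composite through another reaction. Fever is outside step 1 and outside this point. The effect is probably small, but the SAP's own rules discard recorded reactions and the repair is cheap, so it should be made.

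**What to change.** Amend SAP 4.4.1.1.1 to 4.4.1.1.3 as follows.

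- **(a) Pain, headache, malaise, myalgia.** When the investigator's answer is 'Yes', no day is Grade 1 or higher and at least one day is missing, set presence to Yes and maximum intensity to Missing. Count the subject in the numerator and denominator of the 'any' row and in a separate 'Grade missing' row.
- **(b) Erythema, swelling.** Do not count an ungraded 'Yes' as present in the main table. When all measurements are missing, report a 'size missing' count and add a sensitivity row that counts these subjects as present. Keep None where the recorded measurements are below 25 mm, so that one unrecorded day does not turn a small reaction into a case.
- **(c) Maximum.** State in 4.4.1.1.2 that it is taken over non-missing days, subject to (a).
- **(d) Reporting.** Give the number of affected subjects per reaction and group. If it is zero, the tables show that the issue did not arise.

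The cost is a few SAP sentences, a small programming change and some extra table rows. No new data are needed, and some rates may rise slightly.

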***Solicited Reaction:***

A solicited reaction is an event that is prelisted in the CRF. The assessment of these AEs post-vaccination is mandatory. A solicited reaction is defined by a combination of:

- 
- a The term “life-threatening” refers to an event in which the subject was at risk of death at the time of the event; it does not refer to an event which hypothetically might have caused death if it were more severe.
  - b All medical events leading to hospitalizations will be recorded and reported as SAEs, with the exception of: hospitalization planned before inclusion into the study or out-patient treatment with no hospitalization.
  - c “Persistent or significant disability or incapacity” means that there is a substantial disruption of a person’s ability to carry out normal life functions.
  - d Medical and scientific judgment should be exercised in deciding whether expedited reporting is appropriate in other situations, such as important medical events that may not be immediately life-threatening or result in death or hospitalization but may jeopardize the health of the subject or may require intervention to prevent one of the other outcomes listed in the definition above. These should also usually be considered serious. Examples of such events include allergic bronchospasm requiring intensive treatment in an emergency room or at home, blood dyscrasias or convulsions that do not result in inpatient hospitalization, or the development of drug dependency or drug abuse, GBS, new onset diabetes, or autoimmune disease.

- Symptom and
- Onset post-vaccination

Examples of solicited reactions include injection site pain between D0 and D07 post-vaccination or headache between D0 and D07.

A solicited reaction is therefore an AR observed and reported under the conditions (symptom and onset) prelisted (i.e., solicited) in the CRF and considered as related to vaccination.

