**Table 9.1: Solicited injection site reactions: terminology, definitions, and intensity scales**

CRF term (MedDRA lowest level term [LLT])	Injection site pain	Injection site erythema	Injection site swelling
Diary card term	Pain	Redness	Swelling
Definition		Presence of a redness including the approximate point of needle entry	Swelling at or near the injection site Swelling or edema is caused by a fluid infiltration in tissue or cavity and, depending on the space available for the fluid to disperse, swelling may be either soft (typically) or firm (less typical) to touch and thus can be best described by looking at the size of the swelling
Intensity scale*	Grade 1: No interference with activity Grade 2: Some interference with activity Grade 3: Significant; prevents daily activity	Grade 1: $\geq 25$ to $\leq 50$ mm Grade 2: $\geq 51$ to $\leq 100$ mm Grade 3: $> 100$ mm	Grade 1: $\geq 25$ to $\leq 50$ mm Grade 2: $\geq 51$ to $\leq 100$ mm Grade 3: $> 100$ mm

\* For the subjective reaction of pain, subjects or parents / guardians will record the intensity level (Grade 1, 2, or 3) in the diary card. For the measurable reactions of redness and swelling, they will record just the size of the reaction, and the classification as Grade 1, 2, or 3 will be assigned at the time of the statistical analysis

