#### 9.3.2.3.7 Assessment of Causality

The Investigator will assess the *causal relationship* between each unsolicited systemic AE and vaccination as either not related or related, based on the following definitionsa:

- 0: Not related – The AE is clearly / most probably caused by other etiologies such as subject’s underlying condition, therapeutic intervention, or concomitant therapy; or the delay between vaccination and the onset of the AE is incompatible with a causal relationship; or the AE started before the vaccination (screening phase, if applicable)

---

a ICH Guidelines, Clinical Safety Data Management E2A

- 1: Related – There is a “reasonable possibility” that the AE was caused by the vaccination, meaning that there is evidence or arguments to suggest a causal relationship

Note: By convention, all injection site AEs (solicited and unsolicited) and all solicited systemic reactions are considered to be related to vaccination and referred to as reactions, and therefore do not require the Investigator’s opinion on relatedness.

AEs likely to be related to the product, whether serious or not, that persist at the end of the trial will be followed up by the Investigator until their complete disappearance or the stabilization of the subject’s condition. The Investigator will inform the Sponsor of the date of final disappearance of the event.

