4.4.1.1.4 Time of Onset

Time of onset is derived from the daily intensities computed as described in Section 4.4.1.1.1. It corresponds to the first day with intensity of Grade 1, Grade 2, or Grade 3.

Note: If a reaction is not continuous (i.e., reaction occurs over two separate periods of time intervened by at least one daily intensity Missing or None) then the time of onset is the first day of the first occurrence.

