4.4.1.1.5 Number of Days of Occurrence

Number of days of occurrence over the period considered is derived from the daily intensities computed as described in Section 4.4.1.1.1. It corresponds to the number of days with daily intensities of Grade 1, Grade 2, or Grade 3. Number of days of occurrence on the solicited period with a specified intensity may also be derived.

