4.4.1.2 Unsolicited Non-serious AEs

4.4.1.2.1 Presence

An observation will be considered an event if it has at least a verbatim term and is not a Grade 0 intensity event. Grade 0 events should be included in the listing “Unsolicited non-serious adverse events not included in the safety analysis.”

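### SAP 4.4.1.1 uses the 25 mm severity threshold to decide whether injection-site redness or swelling occurred, when it began and how long it lasted; any-size results should be added beside the graded ones.

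*SAP*

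**What the plan says.** **Protocol.** Section 9.3.2.1 introduces the solicited reaction with "A solicited reaction is defined by a combination of" two elements, symptom and onset after vaccination. Size is not one of them. Table 9.1 defines erythema as "Presence of a redness including the approximate point of needle entry". It defines swelling by its location at or near the injection site and adds that size is the best way to describe it, but states no minimum. Subjects record only the size, and the grade is assigned at analysis. Grade 1 begins at 25 mm. Section 9.3.2.2 lists occurrence, time of onset, number of days and intensity as separate items.

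**SAP.** Section 4.4.1.1.1 converts daily sizes with the protocol's scale, treats a reaction too large to measure as Grade 3, and then says: "Note the intensity could be considered “None” (not a reaction) in the analysis despite being considered a reaction by the investigator". Its example is a swelling above 0 mm but below 25 mm. The later sections build on the grade:

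- 4.4.1.1.3: "Presence is derived from the maximum overall intensity on the period considered", with None meaning no presence.
- 4.4.1.1.4, time of onset: "It corresponds to the first day with intensity of Grade 1, Grade 2, or Grade 3".
- 4.4.1.1.5, days: "It corresponds to the number of days with daily intensities of Grade 1, Grade 2, or Grade 3".
- 4.4.1.1.7: ongoing status requires at least Grade 1 on the last solicited day and afterwards. The investigator's own flag is not used.

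For unsolicited events, 4.4.1.2.2 applies the same scale to measurable terms on the solicited list, and 4.4.1.2.1 says: "An observation will be considered an event if it has at least a verbatim term and is not a Grade 0 intensity event". Those graded 0 go to a separate listing.

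**The concern.** A scale written to grade severity has become the test of existence. A subject with 24 mm redness stays in the denominator and is counted as free of erythema, whatever the investigator recorded. Reported onset and days then describe only the part of a reaction at or above 25 mm, under a table label that says simply erythema or swelling.

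The trial's safety objective is to describe the safety profile of each vaccine, so absolute frequency and duration are themselves the result. A reader of the tables would take them to cover all redness and swelling. Pain has no such floor, since any Grade 1 pain counts, so the three injection-site reactions would not be counted on the same footing.

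**Working it through.** The plan states no figure to reproduce. The check sets the definitions against the derivations and then runs the SAP rules on examples.

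**Step 1: does the protocol itself set a size minimum?** Where the protocol wants a threshold in the definition, it puts one there: fever in Table 9.2 is defined as a temperature of at least 100.4°F. The definitions of erythema and swelling in Table 9.1 have none. The 25 mm figure appears only in the intensity row.

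**Step 2: the SAP rules for a size x in mm.**

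- Grade: x < 25 gives None; 25 to 50 gives Grade 1; 51 to 100 gives Grade 2; above 100, or too large to measure, gives Grade 3.
- Presence: the maximum grade over the period is at least 1.
- Onset: the first day with grade at least 1.
- Days: the number of days from D0 to D07 with grade at least 1.
- Overall days, only if ongoing (4.4.1.1.6): (stop date − vaccination date) + days within the period − length of the period + 1. The length is 8 days (D0 to D07).

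**Step 3: application.** The diaries below are invented to show the mechanics and are not trial data. 'Any size' counts every x > 0 as present.

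| Diary, D0 to D07 (mm) | SAP rule | Any size |
|---|---|---|
| A: 10, 20, 24, 20, 15, 10, 5, 0 | absent, 0 days | onset D0, 7 days |
| B: 10, 20, 30, 60, 40, 20, 10, 5 | onset D2, 3 days | onset D0, 8 days |
| C: 10, 20, 30, 60, 40, 30, 26, 24; later maximum 24; stop D10 | onset D2, 5 days, not ongoing | onset D0, ongoing, 10 + 8 − 8 + 1 = 11 days overall |
| D: 10, 20, 30, 60, 60, 50, 40, 30; later maximum 30; stop D12 | onset D2, ongoing, 12 + 6 − 8 + 1 = 11 days overall | onset D0, ongoing, 12 + 8 − 8 + 1 = 13 days overall |
| F: 40, 40, 0, 0, 0, 0, 0, 0 | onset D0, 2 days | onset D0, 2 days |

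A is lost altogether. B loses days at both ends. C also loses its ongoing status. D loses only its first two days, because its end is taken from the recorded stop date. F is unchanged.

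**Step 4: direction and size.** Every subject with a size of 25 mm or more also has a size above 0 mm, so the any-size rate is always at least the reported rate. How far apart they lie depends on the distribution of sizes, which neither document gives.

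**The case against.** The strongest reply is that this is an openly stated convention. The protocol leaves grading to the analysis and offers no class below 25 mm. The SAP applies that scale and spells out the consequence with an example. The rule is identical in all four groups, the safety endpoints are observational with no hypothesis, and a strict > 0 mm rule would count a 1 mm mark at the needle entry point as erythema. All of this stands. It argues against replacing the graded summary, but not against adding the any-size one.

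The protocol's statement that "all injection site AEs (solicited and unsolicited) and all solicited systemic reactions are considered to be related to vaccination and referred to as reactions" is also weaker support than it looks. It is a convention about relatedness and sets no counting rule. The point rests on Table 9.1 and the endpoint list in 9.3.2.2 instead.

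A reader might infer more than the documents support:

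- *That all larger reactions start late and end early.* This happens only when days below 25 mm precede or follow the larger ones (compare B with F). A reaction still at 25 mm or more on D07 and afterwards keeps its recorded stop date in the overall count (D).
- *That small unsolicited reactions vanish.* Under 4.4.1.2.1 they are listed, though outside the analysis tables. Treating a size below 25 mm as Grade 0 is itself a reasonable reading of 4.4.1.2.1 and 4.4.1.2.2 rather than an explicit statement. Redness and swelling starting in D0-D07 are solicited, so only later onsets take this route.
- *That the rule favours one vaccine.* Nothing in the documents shows this. It applies equally to every group, and whether the share of small reactions differs between vaccines is unknown.
- *That adolescents follow another rule*, because the SAP's example mentions adults. Only one scale is given for ages 10 to 55, so the wording is editorial.

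**Conclusion.** The point holds as a mismatch between the protocol's occurrence, onset and duration endpoints and their derivation for erythema and swelling. As planned, those results describe reactions of 25 mm or more, or too large to measure, without saying so. Any-size rates can only be equal or higher, and for an affected subject any-size onset can only be the same or earlier and days in the period the same or more.

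No magnitude can be given. A reader might want a percentage of reactions missed, but any such figure would rest on invented sizes and time courses. The conclusion assumes only that the SAP is applied as written and that some recorded reactions measure between 0 and 25 mm on at least one day. It does not touch the immunogenicity objectives, pain or systemic reactions, and it is not a calculation error. It is an inexpensive improvement worth making.

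**What to change.** 1. Leave the Grade 1 to 3 derivations in SAP 4.4.1.1.1 to 4.4.1.1.7 as they are, and label the erythema and swelling results 'Grade 1 or higher (≥ 25 mm)'.
2. Add supplementary 'any size (> 0 mm)' results for presence, time of onset and number of days for these two reactions, from the daily mm sizes already in the clinical database.
3. Summarise unsolicited injection-site erythema or swelling under 25 mm in the same way, rather than only listing it.
4. As an editorial matter, remove the reference to adults in the 4.4.1.1.1 example or say that the rule covers both age strata.

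No new data are needed and comparability with other results on the same scale is kept. The cost is SAP wording, a second derivation of three variables for two reactions, and a few extra table rows. The any-size rates will look less favourable and may include trivial marks, which is why they should stand beside the graded results and not replace them.
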